15.4.4 Other Exploratory Analyses

Progression-Free Survival and Overall Survival: The Kaplan-Meier estimator will be used to describe the progression-free survival (PFS) and overall survival (OS) experience of patients in each treatment group. These analyses will focus on those patients who have received at least 3 vaccines. PFS is defined as the time between the third vaccine and first documentation of death or disease progression/recurrence. Patients remaining alive without disease progression will have PFS censored at their last follow-up. OS is defined as time between the third vaccine and death. It should be noted that these analyses will focus on only those patients who received Component A alone as we have with other analyses. Additional analyses will describe OS and PFS from randomization.

Radiographic Response: Among the subset of patients with residual disease, the proportion of patients with radiographic response will be estimated with 95% confidence interval.

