6 DEFINITION OF TERMS

Term	Definition
Date of diagnosis	Earliest confirmation by radiographic or histologic examination
Date of randomization	Date TMZ regimen is assigned.
Date of progression	Earliest date of surgical confirmation of disease progression. Where surgery is not feasible, earliest date of radiographic confirmation of progression.
Enrolled patient	Patient who signs the informed consent form and meets all eligibility criteria.

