11.10.2 Follow-up Requirements for Early Withdrawal

Subjects that are withdrawn by the PI prior to randomization will be considered eligibility failures and thus not followed for survival.

Randomized subjects treated on this study that are withdrawn by the PI for any of the aforementioned reasons after the immune monitoring post-vaccine 3 will continue to be followed for progression and survival by the study team until death or are lost to follow up unless the subject voluntarily withdrew permission to follow for survival.

Randomized subjects that withdraw before the immune monitoring post-vaccine 3 will be followed for survival by the study team unless permission to do so has been withdrawn.

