12.3 Physical and Neurological Examination

Physical examinations are to be completed by the investigator or designated participating clinician. The minimum body systems to be examined for any abnormalities and symptoms include: general appearance; skin; lymphatic; head, eyes, ears, nose, throat; extremities; respiratory; cardiovascular; abdominal; musculoskeletal; neurological and genitourinary.

General neurological assessments are to be completed by the investigator or designated participating clinician. The assessment includes but is not limited to: a general

¹³ During vaccine 1: just prior to Component A, 1 and 2 hours after Component A (~20 mL, 1 EDTA lavender top tube and 1 serum red top tube at each blood draw). Just prior to vaccine 2 (1 EDTA lavender top tube, 1 serum red top tube, and 6 yellow ACD tubes). During vaccine 2: 1 and 2 hours after Component A (~20 mL, 1 EDTA lavender top tube and 1 serum red top tube at each blood draw). Just prior to vaccine 3 (9 yellow ACD tubes).

¹⁴ Prior to Td pre-conditioning (~90 mL, 9 yellow ACD tubes and 2 red serum tubes)

¹⁵ At the clinic visit 2 weeks after vaccine 3 [+3 days] (~90 mL, 9 yellow ACD tubes and 2 red serum tubes)

¹⁶ Prior to vaccines #4 and #6 (~90 mL, 9 yellow ACD tubes and 2 red serum tubes)

¹⁷ Immune monitoring blood and pathology testing performed at progression, if possible

¹⁸ Vital signs will be measured at all protocol-indicated visits before and approximately every 30 minutes after vaccination during the post-vaccine monitoring times described in Sections 11.4.2 and 12.6, until discharged from the clinic. Measurements to be reported include temperature in Celsius or Fahrenheit, pulse (beats per minute), respiratory rate (breaths per minute) and blood pressure.

¹⁹ MRI at prior to TMZ cycle 2 clinic visit (within 2 weeks +3 days after vaccine 3)

²⁰ MRI visits take place at the vaccine visit that coincides with the end of TMZ/vaccine cycles 1, 3, 5, 7, 9, 11 and then after every other vaccine visit during the post-TMZ period.

²¹ Pathology testing is performed per BTC standard of care practice and is obtained at the time of new patient evaluation

²² Adverse events and con meds will be collected throughout the study starting with the post-XRT/TMZ screening visit.

mental status examination (orientation, memory, attention/concentration, and language), assessment of cranial nerves, motor, coordination and gait, reflexes, and sensory evaluation.

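### Exploratory PFS is censored at an undefined last follow-up, not at the last disease assessment, so time without imaging can count as progression-free

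*Combined protocol and SAP*

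**What the plan says.** Section 15.4.4 describes PFS and OS by arm with Kaplan-Meier curves. For PFS it sets:

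- Definition: "PFS is defined as the time between the third vaccine and first documentation of death or disease progression/recurrence".
- Analysis set: "These analyses will focus on those patients who have received at least 3 vaccines", limited to Component A alone.
- Censoring: "Patients remaining alive without disease progression will have PFS censored at their last follow-up".
- A further analysis: "Additional analyses will describe OS and PFS from randomization".

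Four other places bear on that censoring date.

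- Section 6 dates progression by surgical confirmation, and failing that by imaging: "Where surgery is not feasible, earliest date of radiographic confirmation of progression".
- Table 3 marks MRI at screening and in the columns for TMZ cycles 2-12 and vaccines 4-20. Its footnote 20 reads "MRI visits take place at the vaccine visit that coincides with the end of TMZ/vaccine cycles 1, 3, 5, 7, 9, 11". Once TMZ is finished, the same footnote keeps scans linked to alternate vaccinations.
- Vaccination can end without progression: at 20 vaccines (11.1), after unacceptable toxicity or urticaria of Grade 2 or more (11.5.4), or for other withdrawal reasons (11.10.1).
- Follow-up outlasts vaccination. Section 11.9 follows evaluable patients for progression and survival. Section 11.10.2 says patients withdrawn after the post-vaccine-3 draw "will continue to be followed for progression and survival by the study team until death or are lost to follow up". Those who withdraw before that draw are followed for survival only.

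**The concern.** A Kaplan-Meier PFS curve treats a patient as known to be progression-free up to the censoring date. Here that date can be a contact at which no disease assessment was made, while progression itself can be dated only from tissue or a scan. After vaccination ends, the plan gives neither a method nor an interval for looking.

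If imaging lapses and contact continues, two things follow. A living patient with undetected progression stays in the risk set as progression-free up to the last contact. A patient who progressed unseen and then died has the event dated at death. Both lengthen PFS.

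At stake is a stated exploratory objective, describing PFS within each arm. Section 9.7 also sets PFS from an earlier vaccine trial against historical controls, and a lengthened curve would mislead that kind of comparison.

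**Working it through.** The documents give no PFS sample size, event count or power, so there is no planned figure to reproduce.

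**1. When does the vaccine-linked scan schedule end?** For a patient continuing TMZ and receiving all 20 vaccines, cycle 2 starts 14 days after vaccine 3 (up to 17), vaccine 4 falls on day 23 (up to day 25), and 16 intervals of 4 to 6 weeks follow.

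- Shortest: 14 + 22 + 16 × 28 = 484 days; 484 / 30.4375 = 15.9 months after vaccine 3.
- Longest: 17 + 24 + 16 × 42 = 713 days; 713 / 30.4375 = 23.4 months.

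**2. Who could outlive it?** Assume exponential PFS from vaccine 3. The share still progression-free at t months is 0.5^(t/m), where m is one of the three PFS medians in sections 7.1 and 9.7.

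| Median m (months) | Share at 15.9 | Share at 23.4 | Of 26 patients |
|---|---|---|---|
| 6.7 | 19% | 9% | 5.0 to 2.3 |
| 15.4 | 49% | 35% | 12.7 to 9.1 |
| 29.2 | 69% | 57% | 17.8 to 14.9 |

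Patients who stop vaccine early add to these.

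**3. How far could the median move?** Simulation of 200,000 patients per scenario. The 6.7-month median is from section 9.7; everything else is assumed: exponential PFS, exponential survival after progression with median 8 months, cutoff at 24 months, early vaccine stops uniform over 0-6 months and unrelated to prognosis, and progression seen when it occurs while vaccination continues. For a patient with no detected progression:

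- stated rule: time = min(death, cutoff), event if death comes first;
- last-scan rule: event at death if death comes first, otherwise censored at the last scan.

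Kaplan-Meier medians in months (true value 6.7; repeat runs agree within 0.1):

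| Stopping early | Stated rule, no scans after stop | Last-scan rule, no scans after stop | Stated rule, 4-monthly scans after stop | Stated rule, 8-weekly scans after stop |
|---|---|---|---|---|
| 10% | 7.2 | 7.0 | 6.9 | 6.8 |
| 20% | 7.6 | 7.2 | 7.1 | 6.9 |
| 30% | 8.2 | 7.5 | 7.4 | 7.0 |

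In the last two columns both rules give the same median to the precision shown; the small excess over 6.7 is delay in detection. In the no-scan columns the stated rule is high by 0.5, 0.9 and 1.5 months and the last-scan rule by 0.3, 0.5 and 0.8. The remainder comes from deaths after unseen progression. Also censoring deaths more than two scan intervals after the last scan brings the median to 6.7 in all three rows.

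**4. The tail of the curve.** Now assume nobody stops early, 8-weekly scans end at 15.9 months, and the data cut is uniform over 12-48 months. At a true median of 15.4 months, 24-month PFS is 0.34; the stated rule gives 0.46 and the last-scan rule 0.34. At 29.2 months, the true value is 0.57; the stated rule gives 0.66 and the last-scan rule 0.49. Past the end of imaging the stated rule reads high, and the last-scan rule can read low.

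**The case against.** The strongest reply is that sections 11.9 and 11.10.2 promise follow-up for progression, not only survival, for patients who reach the post-vaccine-3 draw. A reader might infer that nobody looks for progression once vaccination ends. The documents do not say so: no sentence ends imaging with the vaccine, scans outside the schedule may occur, and 11.10.1 accepts progression documented by physical examination as a reason for withdrawal. Last follow-up could even be read as last progression follow-up. This stands as a limit on the size. It does not remove the gap, because no method or interval is given and the censoring date need not be an assessment.

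A reader might also infer a bias toward one TMZ regimen, or that stopping TMZ stops the scans. Neither is supported. Footnote 20 continues MRIs with the vaccine after TMZ, and MGMT-unmethylated patients keep receiving vaccine after a single TMZ cycle. No figure shows vaccine stopping to differ by arm, and section 15.3 reports no unacceptable toxicity under the revised definition at the time of that amendment.

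The 7.2 to 8.2 month figures are a worst case: the early-stop rates are assumed and nothing is detected after the stop. Last-scan censoring is not free of bias either. Clinical decline is a listed withdrawal reason; if half of early stops fall within 2 months before progression (assumed), last-scan censoring gives 7.0, 7.2 and 7.6 months even with late deaths censored, though the stated rule is higher still.

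Finally, PFS is exploratory and 15.4.4 specifies no test between arms. With 13 patients per arm and a true median of 6.7 months, the simulated 95% sampling range of the median is about 2.8 to 13.3 months, far wider than the shift.

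**Conclusion.** The point holds as a defect in an exploratory analysis. Followed literally, the rule can credit time without assessment as progression-free. The effect on the median is close to zero if imaging continues at about the protocol interval. It is roughly 0.5 to 1.5 months at a true median of 6.7 if imaging lapses entirely in 10% to 30% of patients. These sizes rest on the assumed stopping rates, post-progression survival and cutoff. The direction rests only on imaging lapsing while contact continues.

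The gap is clearest in the additional analysis from randomization. Patients who withdraw before the post-vaccine-3 draw are followed for survival only, so if that analysis includes them, their later progression-free time cannot be verified. The same applies to anyone in the main set who had three vaccines but left before the draw.

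The arms are affected unequally only if vaccine stopping or later imaging differs between them. The primary ELISPOT comparison, the sample size and the safety analysis are unaffected.

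**What to change.** In section 15.4.4, for both the main PFS analysis and the one from randomization:

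- Censor patients alive without documented progression at the date of their last MRI/RANO disease assessment showing no progression.
- Keep death as a PFS event, as defined.
- Report two sensitivity analyses: (a) censoring at last follow-up; (b) censoring deaths that follow a long gap without assessment, with the gap length fixed before analysis. Rule (b) is debatable because the endpoint includes death, so it should not be the main rule.
- Leave OS censored at last contact.
- Report by arm how many patients were still being assessed over time, and do not interpret the curve beyond the period in which scans were made.

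The cost is a few sentences in the plan, provided assessment dates are recorded, and slightly shorter and less precise PFS follow-up. No visit or procedure is added. If scans do continue after vaccination, results will hardly change.

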16 DATA MANAGEMENT AND PROCESSING

16.1 Study Documentation

Study documentation includes but is not limited to source documents, case report forms, monitoring logs, appointment schedules, study team correspondence with sponsors or regulatory bodies/committees, and regulatory documents that can be found in the DCI-mandated “Regulatory Binder”, which includes but is not limited to signed protocol and amendments, approved and signed informed consent forms, FDA Form 1572, CAP and CLIA laboratory certifications, and clinical supplies receipts and distribution records.

Source documents are original records that contain source data, which is all information in original records of clinical findings, observations, or other activities in a clinical trial necessary for the reconstruction and evaluation of the trial. Source documents include but are not limited to hospital records, clinical and office charts, laboratory notes, memoranda, subjects' diaries or evaluation checklists, pharmacy dispensing records, recorded data from automated instruments, copies or transcriptions certified after verification as being accurate copies, microfiches, photographic negatives, microfilm or magnetic media, x-rays, subject files, and records kept at the pharmacy, at the laboratories and at medico-technical departments involved in the clinical trial. When possible, the original record should be retained as the source document. However, a photocopy is acceptable provided that it is a clear, legible, and an exact duplication of the original document.

16.2 Data Management

The subject's medical records will be the primary source document for the study. Source documents include all information in original records and certified copies of original records of clinical findings, observations, or other activities in a clinical investigation used for reconstructing and evaluating the investigation. Source documentations may also include paper eligibility checklists, data flowsheets, patient reported outcomes and other

paper documents. The PI, the study coordinator, the data management team, and the clinical trials manager are permitted to make entries, changes, or corrections in the source documents or database per the study delegation of authority log.

Errors on the source documents will be crossed out with a single line, and this line will not obscure the original entry. Changes or corrections will be dated, signed, initialed, and explained (if necessary). Database changes will be tracked via electronic trail automatically.

16.3 Data Management Procedures and Data Verification

The DCI IT Shared Resource has developed Title 21 CFR Part 11 compliant databases for cancer clinical trials. DCI IT has extensive expertise in database quality assurance, data standards, and use of caBIG tools to support cancer researchers.

Data queries will be generated automatically by the eCRF system. These data queries signify the presence of data inconsistencies. The study and data management team will cross-reference the data to verify accuracy. Missing or implausible data will be highlighted for the PI requiring appropriate responses (i.e., confirmation of data, correction of data, completion or confirmation that data is not available, etc.).

The database will be reviewed and discussed prior to database closure, and will be closed only after resolution of all remaining queries.

16.4 Coding

All medical terms will be coded using CTCAE (version 4.03).

16.5 Study Closure

Following completion of the studies, the PI will be responsible for ensuring the following activities:

- Data clarification and/or resolution
- Accounting, reconciliation, and destruction/return of used and unused study drugs
- Review of site study records for completeness
- Shipment of all remaining laboratory samples to the designated laboratories.

17 ADMINISTRATIVE AND ETHICAL CONCERNS

17.1 Regulatory and Ethical Compliance

This protocol was designed and will be conducted and reported in accordance with the ICH Harmonized Tripartite Guidelines for Good Clinical Practice, the Declaration of Helsinki, and applicable federal, state, and local regulations.

17.2 DUHS Institutional Review Board and DCI Cancer Protocol Committee

The protocol, informed consent form, advertising material, and additional protocol-related documents must be submitted to the DUHS IRB and DCI CPC for review. The study may be initiated only after the Principal Investigator has received written and dated approval from the CPC and IRB.

The Principal Investigator must submit and obtain approval from the IRB for all subsequent protocol amendments and changes to the informed consent form. The CPC should be informed about any protocol amendments that potentially affect research design or data analysis (i.e., amendments affecting subject population, inclusion/exclusion criteria, agent administration, statistical analysis, etc.).

The Principal Investigator must obtain protocol re-approval from the IRB within 1 year of the most recent IRB approval. The Principal Investigator must also obtain protocol re-approval from the CPC within 1 year of the most recent IRB approval, for as long as the protocol remains open to subject enrollment.

17.3 Informed Consent

The informed consent form must be written in a manner that is understandable to the subject population. Prior to its use, the informed consent form must be approved by the IRB.

The Principal Investigator or authorized key personnel will discuss with the potential subject the purpose of the research, methods, potential risks and benefits, subject concerns, and other study-related matters. This discussion will occur in a location that ensures subject privacy and in a manner that minimizes the possibility of coercion. Appropriate accommodations will be made available for potential subjects who cannot read or understand English or are visually impaired. Potential subjects will have the opportunity to contact the Principal investigator or authorized key personnel with questions, and will be given as much time as needed to make an informed decision about participation in the study.

Before conducting any study-specific procedures, the Principal Investigator must obtain written informed consent from the subject. The original informed consent form will be stored with the subject's study records, and a copy of the informed consent form will be provided to the subject. The Principal Investigator is responsible for asking the subject whether the subject wishes to notify his/her primary care physician about participation in the study. If the subject agrees to such notification, the Principal Investigator will inform the subject's primary care physician about the subject's participation in the clinical study.

17.4 Privacy, Confidentiality, and Data Storage

The Principal Investigator will ensure that subject privacy and confidentiality of the subject's data will be maintained. RDSPs will be approved by the appropriate institutional Site Based Research group.

To protect privacy, every reasonable effort will be made to prevent undue access to subjects during the course of the study. Prospective participants will be consented in an exam room where it is just the research staff, the patient and his family, if desired. For all future visits, interactions with research staff (study doctor and study coordinators) regarding research activities will take place in a private exam room. All research related interactions with the participant will be conducted by qualified research staff who are directly involved in the conduct of the research study.

To protect confidentiality, subject files in paper format will be stored in secure cabinets under lock and key accessible only by the research staff. Subjects will be identified only by

a unique study number and subject initials. Electronic records of subject data will be maintained using an electronic database, which is housed by the DCI. Access to electronic databases will be limited to the Principal Investigator, key personnel, statisticians, and the PRTBTC data manager. Data stored on portable memory devices will be de-identified. The security and viability of the IT infrastructure will be managed by the DCI and/or Duke Medicine.

Upon completion of the study, research records will be archived and handled per DUHS HRPP policy.

Subject names or identifiers will not be used in reports, presentations at scientific meetings, or publications in scientific journals.

17.5 Data and Safety Monitoring

Data and Safety Monitoring will be performed in accordance with the DCI Data and Safety Monitoring Plan. The DCI Safety Oversight Committee (SOC) is responsible for annual data and safety monitoring of DUHS sponsor-investigator phase I and II, therapeutic interventional studies that do not have an independent DSMB. The primary focus of the SOC is review of safety data, toxicities and new information that may affect subject safety or efficacy. Annual safety reviews includes but may not be limited to review of safety data, enrollment status, stopping rules if applicable, accrual, toxicities, reference literature, and interim analyses as provided by the sponsor-investigator. For a more detailed description of the DSMP for this protocol, refer to Section [16](#).

17.6 Protocol Amendments

All protocol amendments must be initiated by the Principal Investigator and approved by the IRB prior to implementation. IRB approval is not required for protocol changes that occur to protect the safety of a subject from an immediate hazard. However, the Principal Investigator must inform the IRB and all other applicable regulatory agencies of such action immediately.

Though not yet required, the CPC should be informed about any protocol amendments that potentially affect research design or data analysis (i.e., amendments affecting subject population, inclusion/exclusion criteria, agent administration, etc.).

